## Statistical Analysis Plan

---

unadjusted median, IQR number of red cell transfusions per day in hospital will be reported.

- Proportion of participants surviving up to 30 days without a platelet transfusion will be estimated by the Kaplan-Meier method and compared by treatment arm using Cox regression analysis. The event of interest is time to first platelet transfusion or death. Participants withdrawn or lost to follow up before day 30 will be censored at the time that they withdrew/were lost to follow up.
- Proportion of participants surviving up to 30 days without a red cell transfusion will be estimated by the Kaplan-Meier method and compared by treatment arm using Cox regression analysis. The event of interest is time to first red cell transfusion or death. Participants withdrawn or lost to follow up before day 30 will be censored at the time that they withdrew/were lost to follow up.
- Quality of life at study days 12 and 30 will be assessed using FACT-G and FACT-Th health questionnaires. For the FACT-G subscale scores (physical well-being, social/family well-being, emotional well-being, functional well-being), FACT-G total score and FACT-Th total score, mean (SD) will be calculated and compared by treatment arm using normal regression analysis. For each normal linear regression model, residual plots will be examined. If there is substantial evidence of skew or non-constant variance, log-transformed values will be used instead.

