## Statistical Analysis Plan

Form 9a- Severe bleeding assessment (initial report)	From day R up to study day 30, if severe bleeding is reported on form 7b
Form 9b- Severe bleeding assessment (follow-up report)	When form 9a has been completed
Form 10- Transfusion data form	From day R up to study day 30, if transfusion reported on form 6, form 7, form 12 or form 13
Form 11- Interventions & procedures for daily bleeding	From day R up to study day 30, if indicated on form 7
Form 12- Daily assessments	After day R, up to day 1
Form 1b- Eligibility re-check	Mandatory on day 1
Form 13- Daily assessments	From day 1 to day 30
Form 14- Change to trial treatment administration	From day 1 to day 30, if indicated on form 13
Form 15- Discontinuation of trial treatment	Mandatory for all consented participants
Form 16- Completion of 30 day study observation period	Mandatory for all consented participants
Form 17a- Day 60 (+/- 3 days): follow- up assessments	Mandatory for all consented participants who completed the first 30 days (indicated on form 16)
Form 17b- Day 120 (+/- 14 days): follow-up assessments	Mandatory for all consented participants who completed the first 60 days (indicated on form 17a)
Form 18- Adverse event	From day 1 up to day 60, if applicable
Form 19- Safety outcome: thrombotic events or veno occlusive disease	From consent up to study day 120, if applicable
Form 20- Health questionnaire: EQ-5D-5L	At randomisation, study day 12 (+/- 2 days), study day 30 (+/-2 days), study day 120 (+/- 14 days)
Form 21- Health questionnaire: FACT-Th18	At randomisation, study day 12 (+/-2 days), study day 30 (+/- 2 days)
Form 22a- Health economics	Study day 30 (+/- 2 days)
Form 22b- Health economics	Study day 120 (+/-14 days) or last day of follow-up

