### 4.2 Analysis principles

Unless otherwise specified, all tests will be two-sided and p-values of less than 0.05 will be considered as evidence of a difference between treatment arms.

Multiple comparisons will be performed and this may increase the probability of observing a statistically significant result by chance. No adjustments will be made to account for multiple testing.

P-values will be reported to four decimal places with p-values less than 0.00005 as <0.0001. SAS or R will be used to conduct analyses.

All analyses will be adjusted for the stratification variable (recruitment site). Recruitment site will be accounted for by including a random effect in each model.

All hazard, odds and rate ratios will be presented as active treatment versus placebo. A ratio which is greater than 1 indicates that the hazard, odds or rate is greater in the active treatment arm. 95% confidence intervals will be presented with all ratios. P-values for regression models will be obtained by comparing  $-2 \times \log\text{-likelihood}$  values for models with and without the treatment term.

The key demographics and clinical condition of the participants at consent will be presented for each arm of the trial to describe the cohort. A CONSORT diagram will be presented to show how participants progressed through the trial.

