### 4.8 Procedures for handling Missing Data

For all outcomes, the volume of missing data will be summarised by treatment arm.

Participants withdrawn or lost to follow up before day 30 will be included in the primary outcome analysis (and in secondary outcome analyses where possible), censoring at the time that they withdrew/were lost to follow up.

It is expected that deaths and other safety outcomes, other than for participants withdrawn or lost to follow up, will be fully reported.

For the main analysis of the primary outcome, any missing bleeding assessments during the 30-day follow up period or to the last point of contact, whichever is first, will be assumed to be grade 1 or below. Sensitivity of the primary outcome to missing data will be assessed as per the sensitivity analysis described above.

Missing values for secondary and baseline characteristics will not be imputed. Missing data will be excluded from the relevant analyses.

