## Statistical Analysis Plan

Male			
Age (years)			
Ethnicity			
White			
Asian			
Black African			
Black Caribbean			
Arab/other Middle East ancestry			
Aboriginal			
Other			
Mixed ethnic group:			
White/Black Caribbean			
White/Black African			
White/Asian			
White/Aboriginal			
White/Other			
Other mixed ethnic group			
Height (cm)			
Weight (kg)			
Diagnosis			
AML			
ALL			
APL			
CML			
CLL			
Hodgkins Lymphoma			
Non-Hodgkins Lymphoma			
Myeloma			
MDS			
Other			
Treatment plan			
Induction chemotherapy			
Consolidation chemotherapy			
Autograft			
Allograft			
Other			
Platelet count at consent ( $\times 10^9/L$ )			
Platelet count at randomisation ( $\times 10^9/L$ )			
Haemoglobin at consent (G/L)			
Haemoglobin at randomisation (G/L)			
FACT-G subscale score at randomisation			
Physical well-being			
Social/family well-being			
Emotional well-being			
Functional well-being			
FACT-G total score at randomisation			

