## Statistical Analysis Plan

FACT-Th total score at randomisation			
Medical history			
Diabetes requiring treatment			
Hypertension requiring treatment			
Renal impairment requiring treatment			
Confirmed invasive fungal infection			
Other malignancy			
HLA antibodies			

'Other' diagnoses were xxx and 'other' treatment plans were xxx.

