## Statistical Analysis Plan

FACT-G total score at study day 12 - mean (SD)				
FACT-Th total score at study day 12 - mean (SD)				
FACT-G subscale score at study day 30				
Physical well-being - mean (SD)				
Social/family well-being - mean (SD)				
Emotional well-being - mean (SD)				
Functional well-being - mean (SD)				
FACT-G total score at study day 30 - mean (SD)				
FACT-Th total score at study day 30 - mean (SD)				
All quality of life outcome analyses are adjusted for centre.				

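### The FACT-G and FACT-Th comparisons at days 12 and 30 leave out the same score taken at randomisation and so give up precision the data already hold

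*SAP*

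**What the plan says.** Quality of life is a named secondary efficacy outcome (Protocol 7.2.1, SAP 2.2.1). Protocol 11.5.1 sets out no quality-of-life analysis, so the method comes from the SAP.

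- **Model.** For each FACT score at days 12 and 30, SAP 4.4 states: "mean (SD) will be calculated and compared by treatment arm using normal regression analysis". No covariate is named. If residuals look poor, "If there is substantial evidence of skew or non-constant variance, log-transformed values will be used instead".
- **Adjustment.** SAP 4.2 adjusts every analysis for recruitment site, as a random effect. The footnote to the quality-of-life table in SAP 5.5 adds nothing further: "All quality of life outcome analyses are adjusted for centre".
- **Baseline data.** SAP 3.1, Table 1 schedules the FACT-Th form (Form 21) at randomisation, day 12 and day 30, and Protocol 8.4 agrees. The baseline table in SAP 5.3 lists the four subscales, the "FACT-G total score at randomisation" and the "FACT-Th total score at randomisation" by arm.
- **Missing data.** SAP 4.8: "Missing values for secondary and baseline characteristics will not be imputed". Missing data are left out of the analysis concerned.

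Neither document enters a randomisation score in a model or analyses change from baseline.

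**The concern.** Six scores at two visits make 12 linear regressions. In each, the participant's own earlier score is likely to be a useful predictor of the outcome, and it is already collected. Participants are randomised at a platelet count of 50 × 10⁹/L or below, and treatment starts once the count is 30 × 10⁹/L or below or, for those admitted at that level, after chemotherapy or conditioning begins. The score at randomisation therefore precedes treatment and is a legitimate covariate.

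The silence in SAP 4.4 cannot be read as implied adjustment. Where the SAP wants more than site it says so: a random participant effect for the daily outcomes, and covariate and interaction terms for the subgroups.

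Precision is at stake. Without the baseline score the intervals are wider than the collected data allow, and a chance difference between arms at randomisation is carried into the estimate. There is also a trap in the obvious remedy: with SAP 4.8 as it stands, adding the covariate would remove every participant who has a follow-up score but no randomisation score.

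**Working it through.** **Inputs**

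- Two-sided 5% level (SAP 4.2); 80% power is used as the reference.
- 586 participants, 293 per arm: the required number in SAP 1.5.2 before the 5% addition.
- Full questionnaire completion: assumed.
- Correlation *r* between randomisation and follow-up score, within site: not in the documents; assumed 0.3, 0.5 and 0.7.

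**The plan's own figure.** The documents give no SD, target difference or power for quality of life. The only stated figure used here is 586, which comes from the primary outcome. It reproduces closely:

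- Hazard ratio = ln(0.68)/ln(0.57) = 0.686.
- Events = 4 × (1.960 + 0.842)² / (ln 0.686)² ≈ 221.2, rounded up to 222.
- Mean event proportion = (0.43 + 0.32)/2 = 0.375.
- 222/0.375 = 592, or 590 without rounding the events up. With the hazard ratio taken as 0.685 the result is 585.

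**Gain from adjustment.** In a randomised comparison with a linear model, adding the baseline score multiplies the variance of the treatment difference by 1 − *r*².

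- Cut in standard error = 1 − √(1 − *r*²)
- Equivalent extra participants = 1/(1 − *r*²) − 1
- 95% CI half-width = 1.960 × √(2(1 − *r*²)/293)
- Difference detectable with 80% power = (1.960 + 0.842) × √(2(1 − *r*²)/293)

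The last two are in SD units.

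| *r* | Variance ratio | SE cut | Extra participants | CI half-width | Detectable difference |
|---|---|---|---|---|---|
| not adjusted | 1.00 | – | – | 0.162 | 0.231 |
| 0.3 | 0.91 | 4.6% | 10% | 0.154 | 0.221 |
| 0.5 | 0.75 | 13.4% | 33% | 0.140 | 0.200 |
| 0.7 | 0.51 | 28.6% | 96% | 0.116 | 0.165 |

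**Is the site-only analysis biased?** A simulation used 586 participants, blocked allocation within 27 assumed sites, site as a fixed effect, complete data and 1,500 replicates per setting. The site-only estimate was within 0.006 SD of the truth, with coverage of 95.0% to 95.5%. Adding the baseline score lowered the empirical standard error from 0.081 to 0.077 (*r* = 0.3), 0.085 to 0.073 (*r* = 0.5) and 0.080 to 0.059 (*r* = 0.7). The omission costs precision only.

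**Effect of SAP 4.8.** Let *m* be the share, among participants with a follow-up score, who lack a randomisation score, and suppose these are missing at random.

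- If they are dropped, the variance ratio against site-only is (1 − *r*²)/(1 − *m*). It reaches 1 when *m* = *r*²: 9%, 25% and 49% for the three correlations.
- If the missing covariate is set to the mean over both arms, the ratio is 1 − *r*²(1 − *m*), which stays below 1.

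Example with *r* = 0.3 and *m* = 10% (assumed):

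- Dropped: 0.91/0.90 = 1.011, so the SE rises by 0.6%.
- Mean replacement: 1 − 0.09 × 0.90 = 0.919, so the SE falls by 4.1%.

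A second simulation, with site as a random effect as the SAP specifies (27 sites and intraclass correlation 0.02 assumed, 150 replicates), agreed. Mean standard errors were 0.0816 site-only, 0.0822 with participants dropped, and 0.0782 with mean replacement.

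**The case against.** The strongest reply is that nothing is broken. The analysis respects the site-stratified randomisation, concerns one of eight secondary efficacy outcomes, and leaves the primary and safety results untouched. That stands, and it limits the point to a cheap improvement.

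The size is also uncertain. Some participants are randomised on admission and others after their count has fallen, so the randomisation score may be taken at different stages of treatment and the correlation could be weak. At *r* = 0.2 the cut in standard error is only 1 − √0.96 = 2.0%. The 28.6% figure is the favourable end. This is fair, but a weak correlation costs almost nothing: one degree of freedom per model.

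Full completion at 293 per arm is a best case, since deaths and withdrawals are expected. With 200 per arm the detectable difference is 0.280 SD unadjusted and 0.267, 0.243 and 0.200 SD adjusted. The absolute figures worsen; the proportional gains do not change.

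A chance imbalance at randomisation is sampling error that the confidence interval already covers. That is right, and it is why this is a matter of precision.

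Finally, calling the analysis valid needs a limit: it refers to leaving out the baseline score. The analysis is also complete-case. In an assumed extreme case, where missingness depended on the baseline score in opposite directions in the two arms, the site-only estimate was biased by 0.08 to 0.20 SD and adding the score removed the bias. That is a separate missing-data matter, and a further reason to include the score.

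**Conclusion.** The point holds. All 12 FACT regressions adjust for site alone, although the same scores are collected before treatment and tabulated. Leaving them out neither biases the treatment comparison nor raises its type I error; it widens the intervals. Over assumed correlations of 0.3 to 0.7 the avoidable excess is the difference between a detectable effect of 0.231 SD and one of 0.221 to 0.165 SD, at 293 per arm with full completion. The documents cannot narrow that range. The change should be made because it costs so little, but the planned analysis would still be interpretable without it.

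**What to change.** Make these changes before unblinding:

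1. **SAP 4.4.** Include in each of the 12 models the randomisation value of the same FACT score, alongside the site random effect. If an outcome is log-transformed, transform its covariate in the same way.
2. **SAP 4.8.** Add one exception: a missing randomisation FACT score is replaced by the mean over both arms combined, for use as this covariate only. Take the mean on the scale used in the model. Missing day 12 and day 30 scores stay unimputed.
3. **SAP 5.5.** Change the quality-of-life table footnote to say that the analyses are adjusted for centre and for the matching score at randomisation.

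The primary Cox model needs no change. The cost is wording in two sections and one footnote, with no new data. The one drawback is an exception to the rule against imputing baseline values.

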### Safety outcomes

- Number of thrombotic events from first administration of trial treatment up to and including 120 days after the first dose of trial treatment is received, per day at risk, will be described by arm.
- Number of participants developing Veno-occlusive Disease (VOD; Sinusoidal obstructive syndrome, SOS) within 60 days of first administration of trial treatment, will be described by arm.
- All-cause mortality during the first 30 days and 120 days after the first dose of trial treatment is administered will be estimated by the Kaplan-Meier method and compared using Cox regression analysis. Participants withdrawn or lost to follow up before day 30/day 120 will be censored at the time that they withdrew/were lost to follow up.
- Death due to thrombosis during the first 120 days after the first dose of trial treatment is administered will be estimated using the cumulative incidence function, with the competing risk of death due to other causes. To accommodate a random centre effect, Cox regression analysis will be used to compare death due to thrombosis between treatment arms. Participants who have not died will be censored at day 120 or at the point of last contact, whichever is first. Participants who died prior to day 120 from other causes will be censored at the time of death. If numbers of deaths due to thrombosis are very small, the number of deaths will simply be described by arm.
- Death due to bleeding during the first 30 days after the first administration of trial treatment is received will be estimated using the cumulative incidence function, with the competing risk of death due to other causes. To accommodate a random centre effect, Cox regression analysis will be used to compare death due to bleeding between treatment arms. Participants who have not died will be censored at day 120 or at the point of last contact, whichever is first. Participants who died prior to day 120 from other causes will be censored at the time of death. If numbers of deaths due to bleeding are very small, the number of deaths will simply be described by arm.
- Number of serious adverse events from first administration of trial treatment until 60 days after the first dose of trial treatment is administered, per day at risk, will be summarised by arm, including number of symptomatic thrombotic events (venous thromboembolisms and arterial ischaemic events), veno-occlusive disease, sepsis, organ failure and deaths.

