6.2.6. Discontinuation of Trial treatment

The trial treatment will be permanently discontinued as soon as any one of the following situations occurs:

1. It has been 30 days since the participant first started the randomised trial treatment.
2. The participant has a spontaneous increase in platelet count from $<30 \times 10^9/L$ to $>50 \times 10^9/L$.
3. The participant has had 3 consecutive days with morning platelet counts $>30 \times 10^9/L$, and no requirement for platelet or granulocyte transfusion, or stem cell transplant.
4. The participant receives open label tranexamic acid, other antifibrinolytic agent or procoagulant drug, (e.g., DDAVP, recombinant Factor VIIa, or Prothrombin Complex Concentrates). Use of these agents will be recorded in trial data.
5. The participant begins anticoagulant or antiplatelet therapy.
6. The participant has visible haematuria.
7. The participant has a diagnosis of thrombosis.
8. The participant becomes anuric (defined as urine output $<10 \text{mls/hr}$ over 24 hours).
9. The participant develops sinusoidal obstructive syndrome (SOS, Veno-occlusive Disease, VOD)

Note: If the trial treatment is discontinued it must not be restarted while the participant remains in the trial.

In addition to the reasons stated above participants may stop treatment early or be stopped early for any of the following reasons:

- Disease progression.
- Unacceptable adverse reaction
- Any change in the participant's condition that justifies the discontinuation of treatment in the opinion of the clinician.
- Withdrawal of consent.

In consenting to the trial, participants are consenting to the trial treatment, trial follow up and data collection. As the participant's participation in the trial is entirely voluntary they may choose to discontinue the trial treatment at any time without penalty or loss of benefits to which they are otherwise entitled. Although the participant is not required to give a reason for discontinuing their trial treatment, a reasonable effort should be made to establish this reason whilst fully respecting the participant's rights.

Participants will remain in the trial for the purpose of follow up and data analysis, unless they withdraw their consent from all stages of the trial, in which case, they should be withdrawn. Data collected up until the time of withdrawal will be retained and included in the analysis.

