6.6. Ancillary and post-trial care

There is no reason why participants could not be prescribed therapeutic tranexamic acid after completion of study period (this will be recorded).

7. Trial Outcomes

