All participants who are discharged home before completion of the trial study period (30 days from commencement of the trial treatment) will be asked to complete a daily diary. Participants will be provided with clear guidance notes to assist them in self-assessment of bleeding. They will be asked to respond with a yes/no answer as to whether they have experienced any bleeding on that day.

If a participant reports no bleeding on their bleeding diary this will be recorded as a WHO grade 0 bleed. If the participant does report bleeding they are asked to consult with their haematology care team. If the clinical team consider the bleeding to be significant then the participant should be reviewed and a bleeding assessment will be conducted by a member of the research team. If the haematology team considers the bleeding to be clinically insignificant, this will be recorded as WHO grade 1

Additionally, all participants at home will be contacted by the local research staff on day 30 from first dose of the trial treatment to review the diary and confirm arrangements to collect all completed forms, which will be forwarded on to the data manager for entry into the trial database.

Local research staff completing the daily assessments will receive training and have guide notes to help them collect these data.

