- Trial treatment will be summarised by arm, including number of participants who changed route or frequency, number of participants who missed a dose, reasons for discontinuation of treatment. Median, IQR number of days on trial treatment and on oral trial treatment, from the first day of treatment administration until discontinuation of trial treatment, for participants who received at least one dose of trial treatment, will be estimated using competing risks analysis. Death prior to discontinuation of trial treatment will be considered as the competing risk.
- Number of granulocyte transfusions/participant up to study day 30 will be summarised by treatment arm..
- Location of bleeding up to study day 30 will be summarised, by treatment arm
- Number of participants requiring interventions and procedures for bleeding up to study day 30 will be summarised by treatment arm. This may be sub-categorised by type of intervention or procedure if there are large numbers of participants requiring interventions and procedures.
- Number of participants requiring concomitant medication (categorised as medication increasing risk of bleeding, medication decreasing risk of bleeding, no concomitant medication) up to study day 30 will be summarised by treatment arm. This may be sub-categorised by type of concomitant medication if there are large numbers of participants requiring concomitant medication.
- Number of participants on Mylotarg during the first 30 days of the trial will be summarised by treatment arm.

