**Table xx      Safety data summary - data are numbers**

## Statistical Analysis Plan

Outcome	Active arm (n=)	Placebo arm (n=)	Overall (n=)
Total number of serious adverse events (SAE) up to day 60			
Sepsis			
Organ failure			
GvHD			
Transfusion reaction			
Fever			
Other SAEs			
Number of participants experiencing at least one SAE			
Symptomatic thrombotic events up to day 120			
Venous thromboembolisms			
Arterial ischaemic events			
Veno-occlusive disease up to day 120			
Unexpected adverse reactions up to day 60			
Deaths up to day 120			

All SAEs, unexpected adverse reactions, thrombotic events and veno-occlusive disease are reported in full in Appendix 1.

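### Trial treatment lasts at most 30 days, but no planned thrombosis summary isolates the treated period

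*SAP*

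**What the plan says.** **Treatment.** Protocol 6.2.6 ends trial treatment permanently at the first of several triggers. The latest possible one is "It has been 30 days since the participant first started the randomised trial treatment". An earlier one is platelet recovery ("The participant has had 3 consecutive days with morning platelet counts" above the threshold, without transfusion support). A diagnosis of thrombosis also ends treatment.

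**Thrombosis outcome.** SAP 4.4 (Safety outcomes) and Protocol 11.5.1 plan the "Number of thrombotic events from first administration of trial treatment up to and including 120 days after the first dose of trial treatment", per day at risk, described by arm without a test. Death due to thrombosis is a separate 120-day outcome.

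**Second summary.** The last bullet of the same SAP section, and of the safety list in Protocol 11.5.1, plans a count of serious adverse events to day 60. It is given per day at risk and by arm, and symptomatic thrombotic events are among its components.

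**Table shells.** The interim safety table (SAP 5.1, Table 2) and the final safety data summary (SAP 5.5) have the row "Symptomatic thrombotic events up to day 120". The safety outcomes table in SAP 5.5 also runs to day 120. None has a 30-day or 60-day thrombosis row. The thrombotic event listing in SAP Appendix 1 has no onset date and no last-dose date.

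**Importance and oversight.** Protocol 9.4 names thromboembolism and mortality as the principal safety outcomes and has them sent to the data monitoring committee event by event.

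**After the study period.** Protocol 6.6 states: "There is no reason why participants could not be prescribed therapeutic tranexamic acid after completion of study period", and adds that such use will be recorded. Protocol 8.2.1 equates the study period with 30 days from the start of treatment. SAP 4.5 summarises concomitant medication only to day 30.

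**The concern.** If tranexamic acid raises thrombotic risk mainly while it is taken, the most informative comparison is over the treated days. The planned outcome averages those days with at least three times as many untreated days, in which both arms would be expected to have similar rates. The rate ratio and the per-day rate difference therefore move towards no effect.

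The same SAP section reports all-cause mortality at both 30 and 120 days, and death from bleeding at 30 days, so a 30-day figure is already used for comparable outcomes. Protocol 11.4 gives the low power for thromboembolic events as a reason not to stop early for benefit. Since the extra follow-up is meant to inform on this harm, its summary should show when events occurred relative to treatment.

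**Working it through.** **1. The plan's own figure.** Protocol 11.3.3 and SAP 1.5.3 state that observed venous thromboembolism of 3.6% (placebo) and 5% (tranexamic acid) would exclude a relative risk of 3.5. With 308 per arm:

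- Events: 0.05 × 308 = 15.4 and 0.036 × 308 = 11.09. Ratio 0.05/0.036 = 1.39.
- SE of log ratio = √(1/15.4 − 1/308 + 1/11.09 − 1/308) = 0.386.
- 95% CI = 1.39 × exp(±1.96 × 0.386) = 0.65 to 2.96.

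The statement reproduces. Its time window is not given.

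**2. Share of follow-up off treatment.** With the maximum of 30 treatment days this is 90/120 = 75% over 120 days and 30/60 = 50% over 60 days. With 15 treatment days it is 105/120 = 87.5% and 45/60 = 75%.

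**3. Dilution.** Assume that the excess is confined to treatment time, with on-treatment ratio r. Let s be the share of the window's background events that falls in treatment time. Then

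ratio over window = 1 + (r − 1) × s.

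With a constant background hazard and full follow-up, s = T/W for T treatment days in a window of W days.

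| r | T | Day 1–30 | 60 days | 120 days |
|---|---|---|---|---|
| 3 | 30 | 3.0 | 2.0 | 1.50 |
| 3 | 15 | 2.0 | 1.5 | 1.25 |
| 2 | 30 | 2.0 | 1.5 | 1.25 |
| 2 | 15 | 1.5 | 1.25 | 1.125 |

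**4. Varying the constant-hazard assumption.** The documents give no timing of background thrombosis. If 50% or 75% of 120-day background events fall in treatment time, the 120-day ratio is 1 + 0.5 = 1.5 or 1 + 0.75 = 1.75 for r = 2, and 2.0 or 2.5 for r = 3.

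**5. What this means for step 1.** If the plan's statement refers to 120 days (an assumption), then with s = 0.25 an observed 1.39 corresponds to an on-treatment ratio of 1 + 0.389/0.25 = 2.56. Excluding 3.5 then excludes only an on-treatment ratio of 1 + 2.5/0.25 = 11.

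**6. Expected counts.** Take 3.6% as the 120-day placebo frequency (assumed), 308 per arm, and the interval formula of step 1.

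| s | r | Day 1–30, active v placebo (ratio, 95% CI) | 120 days, active v placebo (ratio, 95% CI) |
|---|---|---|---|
| 0.25 | 2 | 5.5 v 2.8 (2.0, 0.48 to 8.4) | 13.9 v 11.1 (1.25, 0.58 to 2.7) |
| 0.25 | 3 | 8.3 v 2.8 (3.0, 0.78 to 11.6) | 16.6 v 11.1 (1.5, 0.71 to 3.2) |
| 0.50 | 3 | 16.6 v 5.5 (3.0, 1.16 to 7.7) | 22.2 v 11.1 (2.0, 0.99 to 4.0) |

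The excess in events is the same in both windows of each row (about 2.8, 5.5 and 11.1).

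**7. Open-label tranexamic acid after day 30.** Suppose a fraction c of days 31 to 120 in both arms is exposed, with r = 2 and 30 treatment days. The 120-day ratio is [60 + 90(1 + c)]/[30 + 90(1 + c)], which is 1.25 at c = 0, 159/129 = 1.23 at c = 0.1 and 177/147 = 1.20 at c = 0.3. Use in the placebo arm alone would matter more: 150/129 = 1.16 at c = 0.1. The documents give no extent of use and no reason to expect it in one arm only.

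**The case against.** The strongest objections are these.

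- **There is more than one window.** A reader of the table shells might infer that thrombosis is reported only as a 120-day rate. That is not so. The 60-day summary includes symptomatic thrombotic events and dilutes less: a ratio of 3 appears as 2.0, not 1.5. But it is still at least half off treatment, and no table has a row for it. Protocol 9.1 also leaves events already listed as outcomes out of serious adverse event reporting, so this count would have to come from the thrombosis form.
- **The committee is not dependent on the interim table.** A reader might infer that pooling would keep an early excess from the data monitoring committee. Protocol 9.4 has thromboembolic events reported to it as they arise, and it may ask for unblinded data. That stands. The gap is in the by-arm tabulation, at the interim and in the final report.
- **Nothing is hidden.** A longer window lowers a ratio but removes no events, and every event is listed by arm. That stands too. The documents do not support a claim that a clear excess could disappear: with 5.5 against 2.8 events, the early window would not be clear either.
- **The trial is not powered for this.** Both documents say so. It is a reason to keep the new rows descriptive, not a reason to omit them.
- **Analysis on treatment is biased.** Censoring at last dose would be, because a thrombosis itself ends treatment. A fixed day 1–30 window avoids this.

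**Conclusion.** The point holds as a reporting gap. No planned thrombosis summary isolates the treated period; the shortest window is 60 days and has no table row. At least 75% of full 120-day follow-up, and at least half of the 60-day window, is off treatment.

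How far a ratio is diluted depends on three things that the documents do not give: whether any excess is confined to treatment, how long treatment actually lasts, and when background events occur. For an on-treatment ratio of 2, the 120-day ratio ranges from 1.125 (15 treatment days, constant hazard) to 1.75 (three quarters of background events in treatment time). If an excess persists after the last dose, dilution is smaller still, which is a good reason to keep the 120-day total.

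A reader might also take open-label tranexamic acid after day 30 to be a main source of dilution. The documents do not support that: its extent is unknown, and at an assumed 10% to 30% use in both arms it moves the ratio only from 1.25 to between 1.23 and 1.20. It is a minor reporting point.

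**What to change.** 1. In SAP 4.4, and in the safety tables of SAP 5.1 and 5.5, add by arm the number of thrombotic events, the number of participants with an event, and the rate per day at risk for fixed windows of day 1–30 and day 31–120. Place these beside the 120-day total as supplementary descriptive rows without tests, and state how days at risk are counted in each window.
2. Add a row for the 60-day thrombosis count that SAP 4.4 already promises.
3. Add onset day and last-dose day to the thrombotic event listing in SAP Appendix 1.
4. Minor: if open-label tranexamic acid after day 30 is captured as Protocol 6.6 says, tabulate it by arm to day 120. The form list in SAP 3.1 names no specific form for it, so check first that the data exist.

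**Cost.** Items 1 to 3 need SAP wording, several table rows and two listing columns. They should need no new data: Form 19 covers thrombosis to day 120, Forms 13 to 15 cover treatment and its discontinuation, and Protocol 8.5 has the discontinuation date recorded. The price is few events per window and wide intervals, as in step 6 of the working, so the rows should be read as description beside the 120-day outcome, not in place of it.
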